# SYNOPSIS

	· · · · · · · · · · · · · · · · · · ·		
Protocol Title:	A Phase 2, Multicenter, Randomized, Controlled, Double-Masked, Clinical Trial to Evaluate the Efficacy and Safety of OC-01 (varenicline) Nasal Spray in Subjects with Neurotrophic Keratopathy (the Olympia Study)		
Protocol Number:	OPP-102		
Investigational Product:	OC-01 (varenicline) nasal spray, 1.2 mg/mL		
Study Objective:	The objective of this study is to evaluate the safety and effectiveness of OC-01 (varenicline) nasal spray as compared to placebo nasal spray for mean change from baseline in corneal fluorescein staining in subjects with Stage 1 (corneal epithelial hyperplasia/punctate keratopathy) neurotrophic keratopathy (NK) in one or both eyes.		
Overall Study Design			
Structure:	A Phase 2, multicenter, randomized, controlled and double-masked study		
Duration:	Treatment: 8 weeks Follow-up: 1 Week post treatment and 6 months post treatment		
Control:	Placebo (vehicle control) nasal spray		
Dosing Regimen:	Subjects will receive OC-01 (varenicline)/ nasal spray or placebo nasal spray for 8 weeks three times daily (TID) as follows: • OC-01 (varenicline) nasal spray, 1.2 mg/mL		
	
 
Placebo (vehicle control) nasal spray
 
		
Summary of Visit Schedule:	Visit 1- Day 1 - Screening and Randomization Visit 2 (Week 1) - Day 7 ± 2, corneal assessment.		
	Visit 3 (Week 2) - Day $14 \pm 2$ , corneal assessment.		
	Visit 4 (Week 4) - Day $28 \pm 2$ , corneal assessment.		
	Visit 5 (Week 6) - Day $42 \pm 2$ , corneal assessment.		
	Visit 6 (Week 8) - Day $56 \pm 2$ , corneal assessment.		
	Visit 7 (Week 9) - Day $63 \pm 7$ , phone follow-up.		
	Visit 8 (Week 24) - Day 168 ±7, safety follow-up		

Measures Taken to Reduce Bias:	This is a randomized and double-masked study	
Study Population Characteristics		
Number of Subjects:	Approximately 100 subjects (50 subjects per treatment arm)	
Condition/Disease:	Neurotrophic Keratopathy (NK)	
Inclusion Criteria:	Subjects must:	
	1. Be at least 18 years of age at Visit 1.	
	
 
Patients with Stage 1 (corneal epithelial hyperplasia/punctate keratopathy) NK in one or both eyes, as defined by the Mackie Criteria.
 
	
	
 
Evidence of decreased corneal sensitivity (≤ 4 cm using the Cochet-Bonnet aesthesiometer) in at least 1 corneal quadrant.
 
	
	
 
4. Schirmer's test without anesthesia ≥3 mm/ 5 minutes in the affected eye
 
Image: Schirmer's test without anesthesia ≥3 mm/ 5 minutes in the affected eye
 
Image: Schirmer's test without anesthesia ≥3 mm/ 5 minutes in the affected eye
 
Image: Schirmer's test without anesthesia ≥3 mm/ 5 minutes in the affected eye
 
Image: Schirmer's test without anesthesia ≥3 mm/ 5 minutes in the affected eye
 
Image: Schirmer's test without anesthesia ≥3 mm/ 5 minutes in the affected eye
 
Image: Schirmer's test without anesthesia ≥3 mm/ 5 minutes in the affected eye
 
Image: Schirmer's test without anesthesia ≥3 mm/ 5 minutes in the affected eye
 
Image: Schirmer's test without anesthesia ≥3 mm/ 5 minutes in the affected eye
 
Image: Schirmer's test without anesthesia ≥3 mm/ 5 minutes in the affected eye
 
Image: Schirmer's test without anesthesia ≥3 mm/ 5 minutes in the affected eye
 
Image: Schirmer's test without anesthesia ≥3 mm/ 5 minutes in the affected eye
 
Image: Schirmer's test without anesthesia ≥3 mm/ 5 minutes in the affected eye
 
Image: Schirmer's test without anesthesia ≥3 mm/ 5 minutes in the affected eye
 
Image: Schirmer's test without anesthesia ≥3 mm/ 5 minutes in the affected eye
 
Image: Schirmer's test without anesthesia ≥3 mm/ 5 minutes in the affected eye
 
Image: Schirmer's test without anesthesia ≥3 mm/ 5 minutes in the affected eye
 
Image: Schirmer's test without anesthesia ≥3 mm/ 5 minutes in the affected eye
 
Image: Schirmer's test without anesthesia ≥3 mm/ 5 minutes in the affected eye
 
Image: Schirmer's test without anesthesia ≥3 mm/ 5 minutes in the affected eye
 
Image: Schirmer's test without anesthesia ≥3 mm/ 5 minutes in the affected eye
 
Image: Schirmer's test without anesthesia ≥3 mm/ 5 minutes in the affected eye
 
Image: Schirmer's test without anesthesia ≥3 mm/ 5 minutes in the affected eye
 
Image: Schirmer'

	
	acceptable means of birth control (acceptable methods of contraception include hormonal – oral, implantable, injectable, or transdermal contraceptives, mechanical – spermicide in conjunction with a barrier such as a	

Exclusion Criteria:	
 
Subjects must not:
 
1. Have Stage 2 or Stage 3 NK affecting one or both eyes.
 
2. Have ocular graft versus host disease or Stevens-Johnson syndrome.
 

Exclusion Criteria:	
 
Have Stage 2 or Stage 3 NK affecting one or both eyes.
 
Have ocular graft versus host disease or Stevens-Johnson
 

	2. Have ocular graft versus host disease or Stevens-Johnson
	-
	syndrome.
	
 
Have any active ocular infection (COVID-19 conjunctivitis, bacterial, viral, fungal, or protozoal) or active ocular inflammation not related to NK in the affected eye.
 

	6. Be currently receiving autologous serum tears, amniotic membrane, cenegermin, Fresh Frozen plasma or cord blood derived tears.
	
 
Have severe blepharitis and/or severe meibomian gland disease in the study eye.
 

Study Formulations:	Subjects will be randomized 1:1 to receive as a 50 microliter ( $\mu$ L) spray in each nostril:	
	• OC-01 (varenicline) nasal spray, 1.2 mg/mL	
	Placebo (vehicle control) nasal spray	
Randomization:	Subjects who meet the eligibility requirements will be randomly assigned to 1 of 2 treatment groups.	
	The randomization will be stratified by::	
	
 
Pre-procedure (baseline) non-anesthetized Schirmer's score (<5, >5) measured at the screening/randomization visit.
 
	
	A central randomization list will be created using block randomization. Sites will be assigned entire blocks as needed.	
Evaluation Criteria		
Efficacy Measures:	Primary Endpoint	
	• Mean change from baseline in corneal fluorescein staining in subjects with Stage 1 NK at Week 8.	
	Secondary Endpoints	
	
 
Mean change from baseline in visual acuity at Week 8
 
	
Safety Measures:	Adverse event (AE) query	
	Intranasal exam	

Slit lamp biomicroscopy

APPENDIX 3: SPONSOR APPROVALS
APPENDIX 4: INVESTIGATOR'S SIGNATURE

# LIST OF TABLES

	LIST OF ABBREVIATIONS	
Table 3:	Axis Step Sizes for Refinement of Cylinder	47
Table 2:	Refraction Protocol Summary	46
Table 1:	Clinical Grading of Neurotrophic Keratopathy	42

Abbreviation	Term		
AE	Adverse event		
ANCOVA	Analysis of covariance		
BCDVA	Best corrected distance visual acuity		
CAE®	Controlled adverse environment		
CFR	Code of Federal Regulations		
CI	Confidence interval		
CRF	Case report form		
eCRF	Electronic Case Report Form		
EDC	Electronic Data Capture		
EGF	Epidermal Growth Factor		
ETDRS	Early Treatment Diabetic Retinopathy Study		
HGF	Hepatocyte Growth Factor		
HIPAA	Health Information Portability and Accountability Act		
ICF	Informed consent form		
ICH	International Conference on Harmonization		
IRB	Institutional Review Board		
ITT	Intention to Treat		
IUD	Intrauterine device		
MedDRA	Medical Dictionary for Regulatory Activities		
NEI-VFQ	National Eye Institute Visual Function Questionnaire		
Mg	Milligram		
NGF	Nerve Growth Factor		
NK	Neurotrophic Keratopathy		
mL	Milliliter		
μL	Microliter		
Mm	Millimeter		
PED	Persistent Epithelial Defect		
PDGF	Platelet Derived Growth Factor		
SAE	Serious adverse event		
SAP	Statistical Analysis Plan		
STS	Schirmer's Test Score		
TEAE	Treatment-emergent adverse event		
TID	Three times daily		
US	United States		
VAS	Pain Visual Analog Scale		
VEGF	Vascular Endothelial Growth Factor		

# 1. INTRODUCTION

# 2. STUDY OBJECTIVES

The objective of this study is to evaluate the safety and effectiveness of OC-01 (varenicline) nasal spray as compared to placebo for mean change from baseline in corneal fluorescein staining in subjects with Stage 1 (corneal epithelial hyperplasia/punctate keratopathy) NK in one or both eyes.

# 3. CLINICAL HYPOTHESES

This study is testing the hypothesis that OC-01 (varenicline) nasal spray is superior to placebo nasal spray in treating subjects with Stage 1 NK.

# 4. **OVERALL STUDY DESIGN**

Protocol OPP-102 is a Phase 2, multicenter, randomized, controlled, double- masked study designed to evaluate the safety and efficacy of OC-01 (varenicline) nasal spray in subjects with NK. Approximately 100 subjects at least 18 years of age with a physicians' diagnosis of Stage 1 NK, as defined by the Mackie Criteria and meeting all other study eligibility criteria will be randomized 1:1 and will receive OC-01 (varenicline)/ nasal spray or placebo nasal spray for 8 weeks three times daily (TID) as follows:

- OC-01 (varenicline) nasal spray, 1.2 mg/mL
- Placebo (vehicle control) nasal spray

All doses will be delivered as a 50 microliter ( $\mu$ L) nasal spray.

Subjects who terminate early during the application period will be asked to complete safety and/or efficacy assessments (if the subjects agree) prior to study exit. Subjects who are terminated early from the study will not be replaced.

# 5. STUDY POPULATION

# 5.1. Number of Subjects

Approximately 100 subjects (approximately 50 per arm) will be enrolled in approximately 40 sites in the US.

[figure not shown]
# 5.2. Study Population Characteristics

[figure not shown]
All subjects must be at least 18 years of age, of any gender and race and must meet all inclusion criteria and none of the exclusion criteria.

# 5.3. Inclusion Criteria

#### Subjects must:

- 1. Be at least 18 years of age at Visit 1.
- 2. Patients with Stage 1 (corneal epithelial hyperplasia/punctate keratopathy) NK- in one or both eyes, as defined by the Mackie Criteria.
- 3. Evidence of decreased corneal sensitivity ( $\leq 4$  cm using the Cochet-Bonnet aesthesiometer) in at least 1 corneal quadrant.

[figure not shown]
# 5.4. Exclusion Criteria

#### Subjects must not:

- 1. Have Stage 2 or Stage 3 NK affecting one or both eyes.
- 2. Have ocular graft versus host disease or Stevens-Johnson syndrome.
- 3. Have any active ocular infection (COVID-19 conjunctivitis, bacterial, viral, fungal, or protozoal) or active ocular inflammation not related to NK in the affected eye.

- 6. Be currently receiving autologous serum tears, amniotic membrane, cenegermin, Fresh Frozen plasma or cord blood derived tears.
- 7. Have severe blepharitis and/or severe meibomian gland disease in the study eye.

# 5.5. Withdrawal Criteria

If at any time during the study the Investigator determines that a subject's safety has been compromised, the subject may be withdrawn from treatment, but will be followed for safety for the duration of the study, unless they refuse to attend follow-up visits.

Additionally, if a subject should progress to Stage 2 NK while receiving the study drug, the subject should remain in the study and receive treatment. If a subject should progress to Stage 3 NK while receiving study treatment, the subject may be withdrawn from treatment at the discretion of the Investigator. The subject will continue to be followed for safety unless the subject refuses to attend the follow-up visits.

A subject may withdraw consent from the study at any time.

The Sponsor and/or the Investigator may discontinue any subject from study treatment for noncompliance or for any valid medical reason during the study (see Section 8.6.2).

# 6. STUDY PARAMETERS

# 6.1. Efficacy Measures

#### 6.1.1. Primary Efficacy Measure

The following primary endpoints will be tested:

• Mean change from baseline in corneal fluorescein staining in subjects with Stage 1 NK at Week 8.

#### 6.1.2. Secondary Efficacy Measure

The following secondary endpoints will be tested:

• Mean change from baseline in visual acuity at Week 8

# 6.2. Safety Measures

- Adverse events
- Intranasal exam
- Slit lamp biomicroscopy

# 6.3. Other Measures

• Urine pregnancy test (Visit 1, Visit 4 and Visit 6)

# 7. STUDY MATERIALS

# 7.1. Study Drug

# 7.1.1. Regimens

The study drug will be delivered as a 50 microliter ( $\mu$ L) nasal spray in each nostril TID:

- OC-01 (varenicline) nasal spray, 1.2 mg/mL
- Placebo (vehicle control) nasal spray

# 7.1.2. Dispensation Schedule

At Day 1, qualified subjects will be screened and randomized and the first dose of study drug will be administered in the clinic. The remaining administrations will happen at home after the clinic visit.

Between clinic visits, subjects will self-administer OC-01 (varenicline) nasal spray as a 50  $\mu L$  dose in each nostril.

At Visit 2, the study drug/placebo nasal spray will be administered in the clinic to reinforce the proper use of the nasal pump. The remaining administrations will happen at home.

At Week 8, the final study drug/placebo nasal spray administration will occur in the clinic.

Subjects will self-administer OC-01 (varenicline) nasal spray as a 50  $\mu$ L dose in each nostril up to 8 weeks.

# 7.1.3. General Appearance

OC-01 (varenicline)/placebo nasal spray will be formulated at the desired concentration in sodium phosphate buffers and sodium chloride as an aqueous solution and presented in a multi-use preservative-free nasal pump.

The product is preservative-free and intended for intranasal use only. The product should not be used if cloudy or if particulate matter is present.

OC-01 (varenicline) solution must be administered without dilution.

# 8. STUDY METHODS AND PROCEDURES

# 8.1. Subject Entry Procedures

# 8.1.1. Overview

Subjects as defined by the criteria in Section 5.2, Section 5.3 and Section 5.4 will be considered for entry into this study.

#### 8.1.2. Informed Consent

Prior to a subject's enrollment in the trial (i.e., prior to any study-related procedures), the study will be discussed with each potential subject and subject wishing to participate must be administered and provide written informed consent using an Institutional Review Board (IRB)-approved informed consent form (ICF). The ICF must be the most recent version that has received approval by a properly constituted IRB.

#### 8.1.3. Washout Intervals

Prohibited medications, treatments, and activities are outlined in the Exclusion Criteria (Section 5.4).

#### 8.1.4. Procedures for Final Study Entry

Subjects must meet all inclusion criteria and none of the exclusion criteria.

#### 8.1.5. Methods for Assignment to Treatment Groups

Each subject who enters the screening period for the study (defined as the point at which the subject signs the informed consent form (ICF) receives a unique subject identification number before any study-related activities/procedures are performed. This number will be used to identify the subject throughout the clinical study and must be used on all study documentation related to that subject.

The subject identification number must remain constant throughout the entire clinical study.

Subjects who meet the eligibility requirements will be randomly assigned to 1 of 2 treatment groups.

The randomization will be stratified by:

• Pre-procedure (Baseline) non-anesthetized Schirmer's score ( $\leq 5$ , >5) measured at the screening/randomization visit.

A central randomization list will be created using block randomization. Sites will be assigned entire blocks as needed.

# 8.2. Concomitant Therapies

The use of any concurrent medication, prescription or over the counter, is to be recorded on the subject's source document and corresponding eCRF along with the reason the medication was taken.

Concurrent enrollment in another investigational drug or device study during the treatment period is not permitted. Any investigational therapies taken after the treatment period of the study must be recorded on the eCRF.

Subjects on topical ophthalmic medications must have a stable medication regimen for at least 2 weeks prior to enrollment and the regimen must remain unchanged during the treatment period of the study.

#### 8.2.1. Prohibited Medications/Treatments

Disallowed medications/treatments during the study are outlined below:

- No concomitant use of a nicotinic acetylcholine receptor agonist [Nicoderm®, Nicorette®, Nicotrol NS® (nicotine), Tabex®, Desmoxan® (cytisine), and Chantix® (varenicline)] during the treatment period (baseline to Day 56) of the study.
- Topical ophthalmic medications, including preservative free artificial tears must not be utilized for 1 hour pre and post study drug administration.
- Other nasal sprays, including nasal steroids must not be utilized for 1 hour pre and post study drug administration
- Autologous serum tears, amniotic membrane, cenegermin, Fresh Frozen plasma or cord blood derived tears during the study treatment period.

#### 8.2.2. Escape Medications

If a subject should progress to Stage 2 NK while receiving the study drug, the subject should remain in the study and receive treatment. If a subject should progress to Stage 3 NK while receiving the study drug, the subject may be withdrawn from the study treatment at the discretion of the Investigator.

#### 8.2.3. Special Diet or Activities

No special diets or activity is required for this study.

## 8.3. Examination Procedures

# 8.3.1. Procedures to be Performed at Each Study Visit with Regard to Study Objectives(s)

The following procedures will be performed (see Appendix 2 for description)

#### Visit 1 (Day 1): Screening and Randomization

- Informed consent/Health Information Portability and Accountability Act (HIPAA) consent
- Demographic data, medical history, prior medication (s), and ocular history
- Eligibility criteria
- Urine pregnancy test (if applicable)
- NEI-VFQ-25 questionnaire
- Pain Visual Analog Scale (VAS)
- Best corrected distance visual acuity (BCDVA)
- Slit lamp biomicroscopy (prior to Schirmer's Test)

- Corneal fluorescein staining (prior to Schirmer's Test)
- Slit lamp (cornea) photography (prior to Schirmer's Test)
- Corneal sensitivity (prior to Schirmer's Test)
- In-vivo Confocal Microscopy (prior to Schirmer's Test) (select centers)
- Schirmer's Test without anesthesia (pre- treatment)
- Schirmer's Test with anesthesia (concurrent with treatment)
- Intranasal examination (pre- and post- treatment)
- Randomization
- Administration of the study drug/placebo nasal spray (concurrent with Schirmer's test with anesthesia)
- Dispense the study drug/placebo nasal spray
- Concomitant medications
- AE query

#### Visit 2 (Week 1) - Day 7 ±2: 1 Week: Corneal Assessment

- Slit lamp biomicroscopy
- Corneal fluorescein staining assessment
- Slit lamp (cornea) photography
- NK staging per Mackie Criteria
- Schirmer's Test with anesthesia (concurrent with treatment)
- Intranasal examination
- Administration of the study drug/placebo nasal spray (concurrent with Schirmer's test)
- Dispense the study drug/placebo nasal spray
- Concomitant medications
- AE query

#### Visit 3 (Week 2) - Day 14 ±2: 2 Week Corneal Assessment

- VAS
- Slit lamp biomicroscopy
- Corneal fluorescein staining
- Slit lamp (cornea) photography
- Intranasal Examination

- NK staging per Mackie Criteria
- Dispense the study drug/placebo nasal spray
- Concomitant medications
- AE query

#### Visit 4 (Week 4) - Day 28 ± 2: 4 Week Corneal Assessment

- NEI-VFQ-25 questionnaire
- Urine pregnancy test (if applicable)
- NK staging per Mackie Criteria
- VAS
- BCDVA
- Slit lamp biomicroscopy
- Corneal fluorescein staining
- Slit lamp (cornea) photography
- Corneal sensitivity
- Intranasal Examination
- Dispense the study drug/placebo nasal spray
- Concomitant medications
- AE query

#### Visit 5 (Week 6) - Day 42 ± 2: 6 Week Corneal Assessment

- VAS
- Slit lamp biomicroscopy
- Intranasal Examination
- NK staging per Mackie Criteria
- Dispense the study drug/placebo nasal spray
- Concomitant medications
- AE query

#### Visit 6 (Week 8) - Day 56 ± 2: corneal assessment

- NEI-VFQ-25 questionnaire
- VAS
- Urine pregnancy test (if applicable)

- NK staging per Mackie Criteria
- BCDVA
- Slit lamp biomicroscopy (prior to Schirmer's Test)
- Corneal fluorescein staining (prior to Schirmer's Test)
- Slit lamp (cornea) photography (prior to Schirmer's Test)
- Corneal sensitivity (prior to Schirmer's Test)
- In-vivo Confocal Microscopy (prior to Schirmer's Test) (select centers)
- Intranasal examination
- Schirmer's Test with anesthesia (concurrent with treatment)
- Administration of the study drug/placebo nasal spray (concurrent with Schirmer's test)
- Concomitant medications
- AE query

#### Visit 7 (Week 12) - Day 63 ± 7 Phone Visit Follow up

- Concomitant medications
- AE query

#### Visit 8 (Week 24) \_Day 168 ± 7: Safety Follow up

- Intranasal Examination
- Concomitant medications
- AE query

#### **Early Termination**

- Urine pregnancy test (if applicable)
- NEI-VFQ-25 questionnaire
- VAS
- BCDVA
- Slit lamp biomicroscopy (prior to Schirmer's Test)
- Corneal fluorescein staining (prior to Schirmer's Test)
- Slit lamp (cornea) photography (prior to Schirmer's Test)
- Corneal sensitivity (prior to Schirmer's Test)
- In-vivo Confocal Microscopy (prior to Schirmer's Test) (select centers)

- NK staging per Mackie Criteria
- Schirmer's Test with anesthesia
- Intranasal examination
- Administration of the study drug/placebo nasal spray (concurrent with Schirmer's test if subject agrees)
- Concomitant medications
- AE query

# 8.4. Schedule of Visits, Measurements and Dosing

## 8.4.1. Scheduled Visits

Refer to Appendix 1 for a schedule of visits and measurements.

#### 8.4.2. Unscheduled Visits

These visits may be performed to ensure subject safety. All procedures performed at an unscheduled visit will be recorded in the source documents and on the Unscheduled Visit eCRF pages. Any procedure indicated in the eCRF that is not performed should be indicated as "Not done."

Evaluations that may be conducted at an Unscheduled Visit include:

- Slit lamp biomicroscopy
- BCDVA
- Intranasal examination
- Assessment of AEs
- Assessment of concomitant medications and/or treatments
- Any other assessments needed in the judgment of the Investigator.

# 8.5. Compliance with Protocol

Subjects will be instructed on the proper use and storage of the study drug and provided with written instructions upon dispensation of their study drug at Visit 1.

# 8.6. Subject Disposition

## 8.6.1. Treatment Completed Subjects

A Treatment Completed Subject is one who has completed 8 weeks of study visits (Visit 6).

## 8.6.2. Safety Follow up Completed Subjects

A Safety Follow up Completed Subjects is one who has completed all study visits up to Month 6 (Visit 8).

#### 8.6.3. Discontinued Subjects

Subjects may be discontinued from treatment, or from involvement in the study at any time prior to their completion of the study due to:

- Non-fatal adverse event
- Protocol violations
- Disease progression
- Lost to follow-up.
- Physician decision
- Subject non-compliance
- Death
- Study terminated by the Sponsor
- Withdraw by subject (e.g., withdrawal of consent); and
- Other

Note: In addition, any subject may be discontinued from treatment or from study involvement from any sound medical reason at the discretion of the Investigator (after consultation with the Sponsor) or the Sponsor.

Notification of a subject discontinuation and the reason for discontinuation will be made to the Sponsor and will be clearly documented on the eCRF.

If a subject discontinues from treatment, the subject will be asked to be followed for safety for the duration of the study, unless they refuse to attend follow-up visits. A subject will be asked to attend Visit 8 and have all scheduled assessments performed as per the Schedule of Visits and Measurements (Appendix 1)

Discontinued subjects will not be replaced.

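### Protocol 8.6.3 lists disease progression as a ground for leaving the study, at odds with 5.5 and 8.2.2, and does not explicitly ask subjects who stop treatment for the Week 8 staining reading

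*Protocol*

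**What the plan says.** Protocol 8.6.3 covers two kinds of discontinuation with one list: "Subjects may be discontinued from treatment, or from involvement in the study at any time prior to their completion of the study due to". Disease progression is one of the reasons, with no stage attached. A Note gives a further general discretion to stop a subject's treatment or to end study participation, the second of these worded as "from study involvement from any sound medical reason at the discretion of the Investigator (after consultation with the Sponsor) or the Sponsor".

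For those who stop treatment, 8.6.3 says "the subject will be asked to be followed for safety for the duration of the study, unless they refuse to attend follow-up visits". It then names one visit, with a reference to Appendix 1: "A subject will be asked to attend Visit 8 and have all scheduled assessments performed as per the Schedule of Visits and Measurements".

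The rules written specifically for progression are elsewhere. Section 5.5 states that "if a subject should progress to Stage 2 NK while receiving the study drug, the subject should remain in the study and receive treatment", and 8.2.2 repeats this. At Stage 3, 8.2.2 says "the subject may be withdrawn from the study treatment at the discretion of the Investigator". Section 5.5 has the same rule and adds: "The subject will continue to be followed for safety unless the subject refuses to attend the follow-up visits". The general clause in 5.5 is also confined to treatment: "The Sponsor and/or the Investigator may discontinue any subject from study treatment for noncompliance or for any valid medical reason during the study". That clause refers the reader to 8.6.2, which defines subjects who completed safety follow-up. Discontinued subjects are dealt with in 8.6.3.

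**The concern.** The primary endpoint is the change in corneal fluorescein staining at Week 8, read at Visit 6. Progression of NK is a worsening of the disease that the endpoint tracks. If progression can end study participation, or if subjects who stop treatment are not brought back for Visit 6, Week 8 readings go missing for a reason tied to outcome. Discontinued subjects are not replaced, and about 40 sites have to apply the same rule.

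The rest of the plan indicates that progressors were meant to stay. Protocol Appendix 2 has extra gradings for subjects who progress to Stage 2. SAP 5.3 lists two exploratory endpoints at Week 8: progression to Stage 2, and staining change in Stage 2 subjects. Entry requires Stage 1 and excludes Stage 2 or 3 in either eye, so a Stage 2 subject at Week 8 is a progressor. Removing progressors from the study would take out the subjects those endpoints describe.

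**Working it through.** **1. Progression rules side by side.**

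| | 5.5 | 8.2.2 | 8.6.3 |
|---|---|---|---|
| Stage 2 | stay in study, on treatment | same | may leave treatment or study |
| Stage 3 | may stop treatment; safety follow-up continues | may stop treatment; silent on follow-up | may leave treatment or study |

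For Stage 2 the inconsistency covers both treatment and study participation. For Stage 3 it covers study participation only, and it is clear against 5.5.

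**2. What subjects who stop treatment are asked for.** Under Protocol 8.3.1, Visit 8 consists of an intranasal examination, concomitant medications and an AE query. Staining and NK staging are both listed at Visit 6. Section 8.6.3 names the first visit and not the second.

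**3. Gap left by the schedule.** Staining is listed at Visits 1, 2, 3, 4 and 6 (Protocol 8.3.1; SAP 9.11.5), and not at Visit 5. For a subject not seen for staining after Visit 4, the last scheduled reading precedes Week 8 by 56 − 28 = 28 days. With windows of ±2 days at each visit the range is 54 − 30 = 24 to 58 − 26 = 32 days.

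**4. Size, as illustration only.** The documents give no progression or removal rate, so there is no figure to reproduce. Assume that missing Week 8 values are simply left out, with no baseline adjustment, and that progressors differ from other subjects by a gap of 1 to 2 Oxford grades. With n per arm, x progressors per arm and k of them removed:

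shift in arm mean = [x/n − (x − k)/(n − k)] × gap

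The planned arm size is n = 50; x = 5 is assumed.

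- k = 1: 5/50 − 4/49 = 0.0184 × gap
- k = 2: 5/50 − 3/48 = 0.0375 × gap
- k = 3: 5/50 − 2/47 = 0.0574 × gap

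Shift in the treatment difference:

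- equal k in both arms: 0
- 2 against 1: 0.0375 − 0.0184 = 0.0191 × gap, or 0.02 to 0.04 grade
- 3 against 1: 0.0574 − 0.0184 = 0.0390 × gap, or 0.04 to 0.08 grade

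A harsher assumption is that all progressors are removed and their share differs between arms. The shift is then gap × difference in shares:

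- 10% against 5%: 0.05 to 0.10 grade
- 15% against 5%, or 20% against 10%: 0.10 to 0.20 grade

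Only n comes from the documents; x, k, the shares and the gap are assumptions.

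**The case against.** The best reply is that 8.6.3 is a catalogue of disposition reasons and not a set of removal rules. It also contains death and loss to follow-up, which nobody decides, and it does not say that every reason applies to both kinds of discontinuation. Disease progression has a proper use there, namely stopping treatment at Stage 3. The stage-specific rule is stated twice and would ordinarily govern a general list, and SAP 9.7 gives nearly the same list as reasons for discontinuing treatment. The wrong pointer in 5.5 looks like a numbering slip. This is a plausible account of the intent and it weakens the point, but 8.6.3 neither says so nor refers to 5.5.

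Second, follow-up for the duration of the study would ordinarily include Visit 6, and Appendix 1 may say so. That may be right. The stated purpose is nevertheless safety, and the one visit named has no staining.

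Third, the Early Termination visit includes staining and NK staging. That reduces the loss for subjects who leave. Protocol section 4 ties those assessments to study exit, so they do not clearly reach a subject who only stops treatment, and a reading at exit is not a Week 8 reading. Its dependence on the subject's agreement is no special weakness, since any visit depends on that.

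Fourth, the hypothesis concerns Stage 1 subjects, and the visible text does not show how progressors enter the primary analysis. This stands, and it limits what can be said about size.

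A reader might infer more: that the protocol directs sites to remove progressors, that subjects who stop treatment are never seen at Week 8, or that the primary result will be biased. The documents support none of these. The list is permissive, Visit 6 is not excluded, and the text under SAP 14.3 and 14.4 (exploratory endpoints, missing efficacy data) is not visible, so no gap in missing-data handling can be claimed. Nor does the Note on medical discretion need curtailing; it is a general safety provision.

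**Conclusion.** The point holds as an inconsistency and an omission in the wording of 8.6.3. The section lists progression, without a stage limit, as a ground for leaving treatment or the study, which does not agree with 5.5 and 8.2.2. It also does not explicitly request the Week 8 staining reading from subjects who stop treatment. If a site acts on 8.6.3 alone, primary readings can be lost for outcome-related reasons.

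The size and direction of the effect cannot be determined. The illustrations run from 0 to about 0.08 grade with a few unequal removals and up to 0.2 grade under the harsher assumption. All rest on assumed counts and gaps and on missing values being left out. This is a modest point that merits a change because the remedy uses visits already in the schedule. It is conditional on Appendix 1 not already containing the instruction.

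**What to change.** In 8.6.3, state that disease progression is a reason to stop study treatment only, as set out in 5.5 and 8.2.2, and does not by itself end study participation. Correct the pointer in 5.5 from 8.6.2 to 8.6.3.

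Also in 8.6.3, ask subjects who stop treatment before Week 8 to attend the remaining scheduled visits, including Visit 6 with corneal fluorescein staining and NK staging, unless they refuse or withdraw consent. Record any rescue therapy so that the analysis can account for it. Protocol 8.2 already requires concurrent medication and its reason to be recorded, but 8.2.1 bars cenegermin, serum tears and amniotic membrane only during the treatment period, so a subject taken off treatment might receive them before Visit 6. Leave the Note on medical discretion unchanged.

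The cost is a few sentences, plus a few more subjects attending visits that are already scheduled. Some Week 8 readings will then be off treatment or after rescue, and the analysis has to say how it uses them.
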